Glossary of Abbreviations:

MI	Multiple imputation
[REDACTED]	[REDACTED]
NRI	Nonresponder imputation
PASE	Psoriatic arthritis screening and evaluation
PASI	Psoriasis Area and Severity Index
[REDACTED]	[REDACTED]
PGA-F	Physician Global Assessment-Fingernails
PHQ-8	Eight-Item Patient Health Questionnaire
[REDACTED]	[REDACTED]
PP	Per-protocol
[REDACTED]	[REDACTED]
pp-PGA	Palmoplantar Physician's Global Assessment
PPS	Per-protocol set
PSSD	Psoriasis Symptoms and Signs Diary
[REDACTED]	[REDACTED]
QD	Once daily
QoL	Quality of Life
QTcB	QT interval corrected using Bazett's formula
QTcF	QT interval corrected using Fridericia's formula
SAE	Serious Adverse Event
SAP	Statistical Analysis Plan
[REDACTED]	[REDACTED]
sPGA	static Physician Global Assessment
ss-PGA	Scalp specific Physician's Global Assessment
TEAE	Treatment-emergent adverse event
TFLs	Tables, figures, and listings
[REDACTED]	[REDACTED]

1.0 Purpose

The statistical analysis plan (SAP) describes the statistical methods to be used during the reporting and analyses of data collected under BMS Protocol IM011065.

The SAP outlines the following:

- Study design
- Study objectives
- Endpoints and assessments
- Analysis sets
- Statistical methodology
- Conventions and definitions

The SAP should be read in conjunction with the study protocol and case report form (CRF) according to the version on Page 1 of this document. Any further changes to the protocol or CRF may necessitate updates to the SAP. Changes following approval of the first version of the SAP will be tracked in the SAP Change Log and a final version of the updated SAP will be approved prior to final database lock.

2.0 Study Description

2.1 Study Design

This is a 52-week, multi-center, randomized, double-blind, placebo-controlled study to evaluate the safety and efficacy of BMS-986165 vs placebo. A total of approximately 219 qualified subjects with moderate-to-severe plaque psoriasis in mainland China, Taiwan and South Korea will be randomized.

Day 1 activities

Following a screening period of up to 4 weeks, qualified subjects who have completed the screening procedures and have met the inclusion/exclusion criteria will be randomized in a blinded manner in a 2:1 ratio, stratified by country (mainland China, non-mainland China) and previous biologic use for psoriasis, psoriatic arthritis or other inflammatory diseases only (yes/no), via interactive response technology (IRT) to one of the following 2 treatment groups:

- BMS-986165 6 mg once daily (QD)
- Placebo

Dummy tablets (placebo to the BMS-986165 6 mg tablet) will be administered to the subjects to maintain blinding in a double-dummy fashion.

Week 16 activities

The coprimary endpoints, static Physician Global Assessment (sPGA) 0/1 and Psoriasis Area and Severity Index (PASI) 75 will be assessed at Week 16. Subjects receiving placebo will be switched in a blinded manner to BMS-986165 6 mg QD at Week 16. Subjects who are randomized to BMS-986165 6 mg QD will continue on their assigned treatment regimen in a blinded manner.

Week 24 activities

[figure not shown]
Sponsor: Bristol-Myers Squibb
Protocol no: IM011065

During the Week 24 assessment, a subject who has [REDACTED] may be treated with restricted topicals/shampoos as described in Section 6.7.1 of the protocol. These treatments may only be initiated at Week 24, and not at subsequent time points. A subject who is provided these treatments at Week 24 may use them as needed per the investigator's judgement through Week 52.

Study Design elements

The duration of study participation is approximately 60 weeks and will be divided into the following periods: Screening (up to 4 weeks), Treatment (52 weeks), and Follow-up (4 weeks). A schedule of assessments can be found in the protocol. A study design schematic is provided in Figure 1.

Figure 1: Study Design Schematic

Sponsor: Bristol-Myers Squibb
Protocol no: IM011065

2.3 Treatment Assignment and Randomization

At Week 0 (Day 1), subjects who have met all criteria for enrollment will be centrally randomized by a computer-generated randomization schedule in a 2:1 ratio to the following treatments:

- BMS-986165 6 mg QD
- Placebo

The randomization list was generated by the IRT vendor using a permuted block design within each stratum combination level. Randomization will be stratified by country (mainland China, non-mainland China) and previous biologic use for psoriasis, psoriatic arthritis or other inflammatory diseases only (yes/no).

A treatment group will be assigned by IRT based on the above-described randomization schedule and each subject will be assigned a unique randomization number. In addition, a kit (container) number will be assigned by the IRT to the subject corresponding to the treatment assignment. Dummy tablets (placebo to the BMS-986165 6 mg tablet) will be administered to the subjects to maintain blinding.

At Week 16, subjects receiving placebo treatment will be switched in a blinded manner to BMS-986165 6 mg QD. Subjects who are randomized to BMS-986165 6 mg QD will continue their treatment regimen through Week 52.

2.4 Unblinding Information

The Data Monitoring Committee (DMC) provides oversight of safety consideration throughout the study. A separate unblinded team, comprised of an unblinded Independent Reporting Statistician (IRS) and unblinded programmer(s), will produce output for the DMC using masked treatments. Treatment decodes may only be requested by DMC Chair and will be provided by the IRS. Data summaries and listings will be transmitted via a secure portal by IRS to only the DMC members. Additional details regarding the DMC process and unblinding are provided in the DMC charter.

An unblinded analysis of data through Week 16 will be performed after all subjects complete their Week 16 visit or have discontinued prior to Week 16. A select group of personnel who are not involved in the conduct of the study will review the results to write a clinical study report. Following the Week 16 analysis until the end of the study, the investigators, subjects, and clinical trial team members who directly cooperate with the site staff will continue to remain blinded to the initial treatment assignment. Details of maintaining the blind following the unblinded analysis will be finalized prior to the Week 16 database lock. A final analysis will be performed after all subjects complete the Week 52 visit or discontinue prior to the Week 52 visit, and a clinical study report will be written.

Sponsor: Bristol-Myers Squibb
Protocol no: IM011065

2.5 Changes in Statistical Considerations from the Protocol

The following is a list of the important changes in the SAP from the Statistical Considerations section in the protocol:

- Endpoints are revised and 2-point improvement from baseline criterion is added to endpoints Static Physician's Global Assessment (sPGA), Scalp specific Physician's Global Assessment (ss-PGA), Physician's Global Assessment-Fingernails (PGA-F) and Palmoplantar Physician's Global Assessment (pp-PGA)
- The hierarchical testing order for the key secondary endpoints has been updated. The hierarchy presented here supersedes the one that is in the protocol.
- The two endpoints were removed from the list of key secondary endpoints: Change from baseline in Psoriasis Symptom and Sign Diary (PSSD) symptom score and Palmoplantar Physician's Global Assessment (pp-PGA) 0/1 assessed as a proportion of subjects with a pp-PGA score of 0 or 1 among subjects with a baseline pp-PGA score ≥ 3 .
- Imputation methods were updated to remove the prohibited medication/therapy criteria for binary and continuous endpoints.
- The list of relevant protocol deviations provided in the protocol was updated for determination of the Per Protocol population.
- Logistic regression analyses for binary endpoints were removed as these are similar to the CMH analyses.

• [REDACTED]
• [REDACTED]
• [REDACTED]
• [REDACTED]

3.0 Objectives

3.1 Primary Objective

- Assess whether BMS-986165 is superior to placebo at Week 16 in the treatment of subjects with moderate-to-severe plaque psoriasis

3.2 Secondary [REDACTED] Objectives

- Assess whether BMS-986165 is superior to placebo over the first 16 weeks of treatment
- Assess whether BMS-986165 is superior to placebo in scalp psoriasis through week 16 in those subjects who have baseline scalp severity Physician's Global Assessment (ss-PGA) score ≥ 3

Sponsor: Bristol-Myers Squibb
Protocol no: IM011065

- Assess whether BMS-986165 is superior to placebo in nail psoriasis through week 16 in those subjects who have baseline Physician's Global Assessment of Fingernail Psoriasis (PGA-F) score ≥ 3
- Assess whether BMS-986165 is superior to placebo in palmoplantar psoriasis through week 16 in those subjects who have baseline palmoplantar Physician's Global Assessment (pp-PGA) score ≥ 3
- Evaluate improvement in patient-reported outcomes for BMS-986165 compared with placebo through Week 16
- [REDACTED]

4.0 Outcomes

The description of assessments for efficacy and safety can be found in [Section 8](#) of the protocol. The calculation of key measures are provided in [Section 8.2](#) of the SAP.

4.1 Efficacy

4.1.1 Primary Endpoint(s)

The coprimary endpoints for BMS-986165 compared to placebo at Week 16 are defined as:

- sPGA 0/1 response assessed as a proportion of subjects with an sPGA score of 0 or 1 with at least 2-point improvement from baseline
- PASI 75 response assessed as a proportion of subjects who achieve a 75% improvement from baseline in the PASI score

4.1.2 Secondary Endpoint(s)

4.1.2.1 Key Secondary Endpoints for Comparisons to Placebo

The key secondary efficacy endpoints for BMS-986165 compared to placebo at Week 16 are defined as:

- PASI 90 response assessed as a proportion of subjects who achieve a 90% improvement from baseline in PASI score
- sPGA 0 response assessed as a proportion of subjects with an sPGA score of 0
- Scalp specific Physician's Global Assessment (ss-PGA) 0/1 assessed as a proportion of subjects with a ss-PGA score of 0 or 1 with at least a 2-point improvement from baseline among subjects with a baseline ss-PGA score ≥ 3
- PSSD symptom score of 0 assessed as a proportion of subjects with a PSSD symptom score of 0 among subjects with a baseline PSSD symptom score ≥ 1
- PASI 100 response assessed as a proportion of subjects who achieve a 100% improvement from baseline in PASI score
- Dermatology Life Quality Index (DLQI) 0/1 assessed as a proportion of subjects with a DLQI score of 0 or 1 among subjects with a baseline DLQI score ≥ 2

Sponsor: Bristol-Myers Squibb

Protocol no: IM011065

- Physician Global Assessment-Fingernails (PGA-F) 0/1 assessed as a proportion of subjects with a PGA-F score of 0 or 1 with at least a 2-point improvement from baseline among subjects with a baseline PGA-F score ≥ 3

4.2 Safety

The safety outcomes include the following:

- Adverse events (AEs)
 - Treatment-emergent adverse events (TEAEs) – defined as:
 - AEs which occur after the first dose of study treatment through 30 days after the final dose of the study treatment;
 - Treatment-emergent adverse events of interest (AEIs) for the following events:
 - Skin-related AEs
 - Infection AEs, including influenza
 - Creatine kinase (CK) elevation (evaluated as lab toxicity grade 2 or higher)
 - Malignancy
 - SAEs
 - Deaths
- Clinical laboratory parameters

Sponsor: Bristol-Myers Squibb

Protocol no: IM011065

- Absolute and change from baseline values
- Laboratory abnormalities (as determined by Controlled Terminology Criteria for Adverse Events [CTCAE v5.0] grading) presented as the worst postbaseline toxicity group
- Shifts from baseline to maximum postbaseline value
- Potential drug induced liver injury (DILI) is defined as a subject who meets the following criteria:
 - 1) ALT or AST elevation >3 times ULN

AND

 - 2) Total bilirubin >2 times ULN, without initial findings of cholestasis (elevated serum alkaline phosphatase)

AND

 - 3) No other immediately apparent possible causes of liver function test elevation and hyperbilirubinemia, including, but not limited to, viral hepatitis, preexisting chronic or acute liver disease, or the administration of other drug(s) known to be hepatotoxic.
- ALT or AST elevation >5 times ULN
- Vital signs
 - Absolute and change from baseline values
 - Marked abnormalities defined by the below categories:
 - Heart rate:
 - Value > 100 and change from baseline > 30
 - Value < 55 and change from baseline < -15
 - Systolic blood pressure:
 - Value > 140 and change from baseline > 20
 - Value < 90 and change from baseline < -20
 - Diastolic blood pressure:
 - Value > 90 and change from baseline > 10
 - Value < 55 and change from baseline < -10
- Electrocardiograms (ECGs)
 - Absolute and change from baseline values
 - Marked abnormalities defined by the below categories:
 - QT interval corrected using Fridericia's formula (QTcF):

Sponsor: Bristol-Myers Squibb
Protocol no: IM011065

- 450 -< 480 msec
- 480 -< 500 msec
- ≥ 500 msec
- $30 < \text{change from baseline} \leq 60$ msec
- Change from baseline > 60 msec
- Males: < 450 msec, ≥ 450 msec
- Females: < 470 msec, ≥ 470 msec
- PR interval ≥ 200 msec
- QRS interval ≥ 120 msec

In cases where the QT interval corrected using Bazett's (QTcB) formula is captured instead of QTcF, then the uncorrected QT will be converted to QTcF for analyses.

- Eight-Item Patient Health Questionnaire (PHQ-8) total score
 - Absolute and change from baseline values
 - Shifts from baseline scores
- Electronic Columbia-Suicide Severity Rating Scale (eC-SSRS)
 - Suicidal ideation and suicidal behavior responses by visit
 - Shifts from baseline to postbaseline value for suicidal ideation and suicidal behavior
 - Worst postbaseline value for suicidal ideation and behavior

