• Assess whether BMS-986165 is superior to placebo at Week 16 in the treatment of subjects with moderate-to-severe plaque psoriasis	• sPGA 0/1 • PASI 75
Selected Secondary Endpoints	
• Assess whether BMS-986165 is superior to placebo over the first 16 weeks of treatment	• sPGA 0/1 [REDACTED] • PASI 90 • sPGA 0 • PASI 100 [REDACTED]
• Evaluate improvement in patient reported outcomes for BMS-986165 compared with placebo through Week 16	• Change from baseline in Psoriasis Symptoms and Signs Diary (PSSD) symptom score [REDACTED] [REDACTED] • PSSD symptom score of 0 (among subjects with a baseline PSSD symptom score ≥ 1) [REDACTED]

Overall Design:

This will be a 52 week, multicenter, randomized, double-blind, placebo-controlled study in subjects with stable moderate-to-severe plaque psoriasis. Subjects will undergo screening evaluations within 28 days prior to administration of study treatment to determine eligibility. Following the screening process, approximately 219 subjects will be randomized in a 2:1 ratio to either BMS-986165 6 mg QD or placebo, respectively.

Randomization should not occur until at least 8 days after the screening visit to allow collection of PSSD data during screening in order to calculate a baseline PSSD score. Randomization will be stratified by country (mainland China vs. non-mainland China) and previous biologic use (for psoriasis, psoriatic arthritis or other inflammatory diseases only; yes/no).

At Week 16, subjects randomized to placebo from screening through the Week 16 visit will be switched to BMS-986165 6 mg QD through Week 52 in a blinded manner, so that subjects who had been randomized to placebo will not know if they had been randomized to BMS-986165 or to

placebo post-screening. Subjects randomized to BMS-986165 6 mg QD will continue their current dose through Week 52.

At Week 24, a subject with sPGA ≥ 3 may be treated with restricted topical medications, such as topical high potency corticosteroids (WHO Classes I-V) but only at this time point and at the discretion of the investigator. This treatment may be continued through end of study.

Subjects who discontinue study treatment early are expected to remain in the study for continued follow-up until Week 52.

Subjects completing 52 weeks of treatment may be eligible to roll over to a separate long-term extension study and be treated with open-label BMS-986165 6 mg QD.

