8.2.1 Adverse Events of Interest

Adverse events of interest (AEIs) are AEs for a particular product or class of products that a Sponsor may wish to monitor carefully. Adverse events of interest may be serious or non-serious. Such events may require further investigation to better characterize and understand them. In the BMS-986165 clinical development program, certain skin-related AEs (eg, acne), infection AEs, and CK elevation have been identified as potential AEIs; however, there has been no definitive assessment on the causal relationship between these events and treatment with BMS-986165. Additionally, given a potential association between treatment for autoimmune diseases and increased risk for cancer, malignancy has been identified as a potential AEI. Therefore, additional information about certain skin-related AEs, infection AEs, CK elevation, and malignancy may be collected on the case report form in order to better characterize and understand them.

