9.5.1 Adverse Events

Treatment-emergent adverse events (TEAEs), SAEs and deaths, and AEs leading to study treatment discontinuation, AEs by maximum severity, and AEs by relationship will be summarized by the MedDRA system organ class and preferred term. All TEAEs, AEIs, as well each AE adjudicated category (ie, infections, cardiovascular, and suicidal ideation and behavior) will also be summarized by preferred term sorted by decreasing frequency.

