6.2.1 Adverse Events

Adverse events will be presented for the number and percentage of subjects and the number of events. Treatment-emergent will be provided in listings. Summary tables will be reported in decreasing frequency based on the total column. Counting for frequency analysis will be by subject and not by AEs, and subjects are only counted once for recurring AEs within each system organ class (SOC) or preferred term (PT); however, the number of total AEs per subject, including multiple occurrences of individual AEs, will also be presented. For summaries of severity, AEs will be reported only at their maximum severity in each subject. Subjects with multiple AEs within a particular SOC or PT will be counted under the category of their most severe event within that SOC or PT.

AE (including deaths) dates will be imputed according to algorithms detailed in [Section 8.0](#). The imputed date of AE onset will be used to assess whether AEs should be considered as treatment-emergent and included in the safety summaries. The original, partial dates will be included in data listings. No imputation will be performed on missing AE seriousness, severity, or relationship; they will be reported as missing.

AEs will be included in a period if the start date of the AE is after the first dispensation date within a period.

An overall summary for the following categories will be presented:

- Deaths
- SAEs
- Related SAEs
- AEs
- Related AEs
- Discontinued treatment due to AEs

The following summaries will also be provided for the following:

- TEAEs by SOC and PT
- Treatment-related TEAEs by SOC and PT

Sponsor: Bristol-Myers Squibb

Protocol no: IM011065

- TEAEs by PT reported in $\geq 5\%$ of subjects
- TEAEs by PT reported in $\geq 1\%$ of subjects
- Treatment-related TEAEs by PT reported in $\geq 5\%$ of subjects
- TEAEs categorized by severity by SOC and PT
- Exposure-adjusted incidence rate (EAIR) for TEAEs by SOC and PT – EAIR is defined in [Section 8.1](#) of the SAP.

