6.2.1.1 Adverse Events of Interest (AEI) and Other Important AEs

Summaries for treatment-emergent AEIs events will be provided by PT for each AEI category.

- Skin-related events
- Infection events
- Malignancy events

Creatine kinase (CK) elevation for CK elevation > 2.5 upper limit of normal will be summarized as CTCAE grade 2 or higher in the clinical laboratory summaries.

Additional information collected for some events as part of the clinical safety program and adjudicated events will also be summarized.

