6.2.1.2 Serious Adverse Events

Summaries for treatment-emergent SAEs will be provided for the following:

- Treatment-emergent SAEs by SOC and PT

6.2.1.3 Adverse Events Leading to Discontinuation of Study Treatment or Study Treatment Interruption

Summaries for TEAEs leading to discontinuation of study treatment will be provided for the following:

- TEAEs by SOC and PT

Summaries for TEAEs leading to study treatment interruption will be provided for the following:

- TEAEs by SOC and PT

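### The malignancy and SAE tables stop counting 30 days after the last dose, although subjects who stop early are followed, and their events collected, to Week 52

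*SAP*

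**What the plan says.** **Analysis (SAP).** Section 4.2 sets the treatment-emergent window as "AEs which occur after the first dose of study treatment through 30 days after the final dose of the study treatment". The same section brings the events of interest under that window: "Treatment-emergent adverse events of interest (AEIs) for the following events", with malignancy in the list. Section 6.2.1.1 follows suit: "Summaries for treatment-emergent AEIs events will be provided by PT for each AEI category", malignancy being one of three categories. Section 6.2.1.2 does the same for serious events: "Summaries for treatment-emergent SAEs will be provided for the following", the single table being by system organ class and preferred term.

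Three other places bear on late events:

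- Section 6.2.1 uses the onset date to decide whether an AE is treatment-emergent and belongs in the safety summaries. It then plans an overall summary whose rows for SAEs and AEs carry no treatment-emergent label. On listings it says "Treatment-emergent will be provided in listings".
- Section 6.2.1.1 promises a summary of additional information gathered on some events under the clinical safety program, and of adjudicated events. It names neither the events nor a window.
- Section 6.2.2 lists every fatal AE, with no window.

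**Collection (Protocol).** The Synopsis states: "Subjects who discontinue study treatment early are expected to remain in the study for continued follow-up until Week 52". Section 8.2.2 collects nonserious AEs to the subject's final visit. It collects SAEs to 30 days after the last dose, or to the end of participation if the last scheduled visit is later. Section 8.2.1 gives the reason for watching cancer: "given a potential association between treatment for autoimmune diseases and increased risk for cancer, malignancy has been identified as a potential AEI". Section 9.5.1 plans summaries by preferred term of "All TEAEs, AEIs, as well each AE adjudicated category" and states no time limit.

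**The concern.** The trial keeps early stoppers under observation and records their adverse events, but the two tables in which a reader would look for cancers and serious events close 30 days after the last dose. Malignancy is the event of interest for which a short window is hardest to defend, because the protocol's reason for watching it is a possible increase in cancer risk, and nothing in that reason confines the interest to the month after the last dose. In a trial of about 219 subjects, malignancy counts will be very low, so leaving out one case could change the named table from one event to none. Late SAEs of other kinds are left out of the SAE table by the same rule.

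**Working it through.** The plan states no figure to reproduce here. The check compares the two time windows and then sizes the difference.

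**1. Inputs**

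- End of counting: last dose day L + 30 (SAP 4.2).
- End of follow-up: Week 52, target Day 365 (SAP 8.5).
- Safety follow-up visit: Day 393 (SAP 8.5).
- Planned sample: about 219 subjects (Protocol 4.2).
- Discontinuation rate and malignancy rate: not given in the documents.

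**2. Uncounted follow-up for one subject who stops and stays to Week 52**

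Uncounted days = max(0, 365 − (L + 30))

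| Last dose day L | Counting ends | Uncounted days to Day 365 |
|---|---|---|
| 1 | 31 | 334 |
| 57 (Week 8) | 87 | 278 |
| 113 (Week 16) | 143 | 222 |
| 225 (Week 32) | 255 | 110 |
| 335 | 365 | 0 |

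The gap closes at L = 365 − 30 = 335. If an early stopper also attends the Day 393 visit, up to 393 − 365 = 28 further days fall outside the window. A completer with a last dose on Day 365 is counted to Day 395, past the Day 393 visit, and loses nothing.

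**3. Total follow-up outside the window (assumed range)**

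Assume that 5%, 10% or 20% of 219 subjects stop early, at times spread evenly over Days 1 to 364, and that all of them are followed to Day 365. The mean gap is then 153.7 days.

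- 5%: 11 subjects × 153.7 / 365.25 = 4.6 person-years
- 10%: 22 × 153.7 / 365.25 = 9.3 person-years
- 20%: 44 × 153.7 / 365.25 = 18.5 person-years

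Taking every stop at about Week 26 gives nearly the same: 182 − 30 = 152 days each.

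**4. Expected malignancies outside the window (assumed range)**

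At an assumed 0.5 to 1 malignancy per 100 person-years, the result runs from 4.6 × 0.005 = 0.02 to 18.5 × 0.01 = 0.19 cases. The rate is illustrative only.

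**5. Where a late, non-fatal malignancy would appear**

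| Output | Late event included? |
|---|---|
| Malignancy event-of-interest table (SAP 6.2.1.1) | No |
| SAE table (SAP 6.2.1.2) | No |
| SAE and AE rows of the overall summary (SAP 6.2.1) | Unclear: rows unlabelled, but the entry rule in that section points to treatment-emergent events |
| Additional-information summary (SAP 6.2.1.1) | Unclear: events and window unnamed |
| AE listing (SAP 6.2.1) | Unclear: the sentence lacks a noun and does not exclude other listings |
| Death listing (SAP 6.2.2) | Only if the event is fatal |

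**The case against.** The strongest reply is that a 30-day window is a coherent choice. It matches the exposure-adjusted incidence rate in SAP 8.1, which gives 30 days beyond treatment to event-free subjects who discontinue, and to event-free completers who do not roll over. Numerator and denominator therefore agree. It also matches the basic 30-day term for SAE collection in Protocol 8.2.2, and completers are unaffected. All of this stands, and is why the existing tables should stay.

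Other parts of the reply limit how far the point can go. A reader might infer any of the following, and the documents do not support them:

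- **That a late malignancy enters no summary at all.** The overall-summary rows are unlabelled. The additional-information sentence could also reach malignancy without any adjudication committee, since Protocol 8.2.1 names malignancy among the events on which extra case report form data may be collected. This is ambiguity, not exclusion.
- **That a late malignancy is listed only if fatal.** The listings sentence does not say so, and the visible SAP gives no complete inventory of listings.
- **That a cancer diagnosed after stopping is always missed.** SAP 6.2.1 classifies by onset, not diagnosis. Protocol Appendix 3 has an abnormal finding reported as an AE until a diagnosis is known, and the term then updated. A cancer whose first reported finding arose on treatment could keep an on-treatment onset and be counted.
- **That the SAP departs from the protocol without declaring it.** Protocol 9.5.1 states no window, and silence is not a commitment to count to end of study. Part of the change list in SAP 2.5 is redacted, so an undeclared change cannot be shown.

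Follow-up may also fall short of Week 52. Protocol 7.1.2 requires continued follow-up but says only that stoppers should be encouraged to attend the Week 52/Early Termination and safety visits. The person-years above are therefore close to an upper limit for each assumed rate. None of this removes the core: the two named tables carry an explicit limit shorter than the collection period.

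**Conclusion.** The point holds in a limited form. For a subject who stops early, a malignancy or SAE with onset more than 30 days after the last dose is outside the malignancy table and the SAE table, although the protocol provides for its collection. Its place in the other outputs is not settled by the text.

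The size per subject is firm: up to 222 days for a last dose on Day 113, up to 334 days at the extreme, and nothing to Day 365 from a last dose on Day 335 onward. The size for the trial is not. The 4.6 to 18.5 person-years rest on an assumed 5% to 20% early discontinuation, even stopping times and complete follow-up. The expected number of malignancies in that time is probably well below one. The documents therefore do not support saying that the malignancy risk will be understated, only that the named tables could miss a case. The point merits action because the remedy is cheap and because, for a rare event that the sponsor chose to monitor, one case matters.

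**What to change.** 1. Keep the treatment-emergent tables and the matching exposure-adjusted rate as they are.
2. In SAP 4.2, 6.2.1.1 and 6.2.1.2, add one summary and one listing of malignancy events of interest and SAEs with onset from first dose to end of study. Flag each event as within or beyond 30 days of the last dose, and show it under the last treatment received before onset. Keep placebo subjects who never switched separate.
3. If a rate is given for this summary, use time at risk to end of study, not treatment time plus 30 days, and divide it at the switch for placebo subjects who crossed over.
4. In SAP 6.2.1, state whether the SAE and AE rows of the overall summary are limited to treatment-emergent events, and complete the sentence on listings. In 6.2.1.1, name the events and the window for the additional-information summary.

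The cost is a few lines of SAP text, one table and one listing, all from data already collected. The downside is that late events are less clearly attributable to study drug; the 30-day flag lets the reader see which they are.
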